5.1 Recruitment

A CONSORT flow diagram will be used to summarise the number of patients who were:

- registered
- lost to follow-up*
- withdrew*
- included in the final primary analysis
- excluded from the final primary analysis*

*reasons will be provided

5.2 Baseline patient characteristics

Patients will be described with respect to age, gender, cancer stage at diagnosis, anatomical site of malignancy, etc. Categorical data will be summarised by numbers and percentages. Continuous data will be summarised by mean, SD and range if data are normal and median, IQR and range if data are skewed. Minimum and maximum values will also be presented for continuous data.

6. Definitions of endpoints for analysis

Given that only one patient was recruited into Arm A, no analysis will be conducted on Arm A patients and all subsequent sections will refer to Arm B patients.

Pseudovirus neutralisation results are provided as continuous values, and currently there is limited research suggesting where the cut-off should lie in order to dichotomise the measurements into positive\negative neutralisation. Based on preliminary exploratory analysis run by the lab team at St. George's Hospital, we will dichotomise the pseudovirus neutralisation results using two different cut-offs: 0.5 and 0.8. Any endpoint involving pseudovirus neutralisation will be reported using each different cut-off.

Descriptive analysis on pseudovirus neutralisation results (summary statistics and boxplot by timepoint) will be included in the report.

6.1 Primary endpoint

Proportion of patients at each sample timepoint (D0, D28, D56, D84) with a positive detection of IgG specific antibodies to SARS-CoV-2 (nucleocapsid and spike-protein). As part of a complete-case sensitivity analysis, proportions will be reported to include only patients who had a blood test at all timepoints.

6.2 Secondary endpoints

6.2.1 Unvaccinated patients

- Proportion of participants at each timepoint with a positive detection of IgG specific antibodies to SARS-CoV-2 (nucleocapsid and spike-protein).
- Geometric fold rise (GMFR) in geometric concentration (GMC) of spike-protein antibodies from the first timepoint with a positive antibody detection to each following timepoint, in antibody positive patients. If data required to analyse this endpoint is not available at the time of primary analysis, the analysis for this endpoint will be postponed until the data is provided.

6.2.2 Vaccinated patients

- Proportion of participants at each timepoint with a positive detection of (i) IgG specific antibodies to SARS-CoV-2 (spike-protein) and (ii) pseudovirus neutralisation. As part of a sensitivity analysis, proportions will be reported at each timepoint to include only patients who had not received a positive nucleocapsid detection up to and including that timepoint.

- Proportion of participants with a positive detection of (i) IgG specific antibodies to SARS-CoV-2 (spike-protein) and (ii) pseudovirus neutralisation at time periods adjusted to the no. of days from 1st vaccine date. As part of a sensitivity analysis, proportions will be reported at each time period to include only patients who had not received a positive nucleocapsid detection up to and including that time period.
- Geometric fold rise (GMFR) in geometric concentration (GMC) of spike-protein antibodies from the D0 sample timepoint to each post-D0 timepoint. If data required to analyse this endpoint is not available at the time of primary analysis, the analysis for this endpoint will be postponed until the data is provided.

6.3 Exploratory endpoints

6.3.1 Vaccinated/Unvaccinated patients

The following endpoints will be reported separately for (i) vaccinated and (ii) unvaccinated patients, and (iii) across all patients.

- Sensitivity: Proportion of participants with a positive detection of IgG specific antibodies to SARS-CoV-2 (spike protein) out of those who had a positive neutralisation detection from the pseudovirus assay, at each timepoint.
- Specificity: Proportion of participants at each timepoint with a negative detection of IgG specific antibodies to SARS-CoV-2 (spike protein) out of those who had a negative neutralisation detection from the pseudovirus assay, at each timepoint.

6.3.2 Vaccinated patients with a second dose

- Geometric fold rise (GMFR) in geometric concentration (GMC) of spike-protein antibodies from baseline (pre-second dose) to each timepoint (post-second dose). If data required to analyse this endpoint is not available at the time of primary analysis, the analysis for this endpoint will be postponed until the data is provided.
- GMFR of neutralising geometric mean titres (GMT) of spike-protein antibodies from baseline (pre-second dose) to each timepoint (post-second dose). If data required to analyse this endpoint is not available at the time of primary analysis, the analysis for this endpoint will be postponed until the data is provided.

6.3.3 Other exploratory endpoints

The following endpoints are also planned to be performed:

- Investigate antigen dynamics over time to compare with quantitative RT-PCR (Arm A)

- To examine HLA-KIR interactions that shape CD8 anti-viral responses (Arms A & B)
- To explore the relationship between host immune genotype (e.g., HLA-KIR) and peripheral blood (Arms A & B) immune cell phenotype with viral clearance (Arms A & B)
- To investigate blood immune cell activation and transcriptome in participants (Arms A & B)

Due to the rapidly evolving nature of the COVID-19 pandemic, these exploratory endpoints are no longer relevant to this study. As the focus of the study has shifted towards exploring the serological responses following SARS-CoV-2 infection or vaccination (1,2), these exploratory endpoints will no longer be performed.

7. Analysis methods for endpoints

7.1 Primary endpoint

At each sample timepoint (D0, D28, D56, D84), the proportion of patients with a positive detection of (i) nucleocapsid antibodies and (ii) spike-protein antibodies will be reported alongside an exact two-sided 95% confidence interval. For the sensitivity analysis, the proportions will be reported in a similar manner except the denominators and numerators used to calculate each proportion will only include patients who had blood test results available at all timepoints (D0, D28, D56, D84).

7.2 Secondary endpoints

7.2.1 Unvaccinated patients

- At each sample timepoint (D0, D28, D56, D84), the proportion of patients with a positive detection of (i) nucleocapsid antibodies and (ii) spike-protein antibodies will be reported alongside an exact two-sided 95% confidence interval.
- *Geometric fold rise (GMFR) in geometric concentration (GMC) of spike-protein antibodies from the first timepoint with a positive antibody detection to each following timepoint, in antibody positive patients.* A scatterplot will be produced to plot the GMFR in GMC of antibodies against sample timepoints (D0, D28, D56, D84) in antibody positive patients. For each patient, the first data point to be plotted will be at the first sample timepoint at which they showed a positive antibody detection.

7.2.2 Vaccinated patients

- For all patients who received at least one dose prior to D0, at each sample timepoint (D0, D28, D56, D84), the proportion of patients with a positive detection of (i) spike-protein antibodies and (ii) pseudovirus neutralisation will be reported alongside exact two-sided 95% confidence intervals. For the sensitivity analysis, the proportions will be reported in a similar manner except the denominators and numerators used to calculate each proportion will only include patients who had not received a positive nucleocapsid detection up to and including that timepoint.
- At each time period (adjusted to the no. of days from 1st vaccine date), the proportion of patients with a positive detection of (i) spike-protein antibodies and (ii) pseudovirus neutralisation will be reported alongside an exact two-sided 95% confidence interval. For the sensitivity analysis, the proportions will be reported in a similar manner except the denominators and numerators used to calculate each proportion will only include patients who had not received a positive nucleocapsid detection up to and including that timepoint.

- *Geometric fold rise (GMFR) in geometric concentration (GMC) of spike-protein antibodies from the D0 sample timepoint to each post-D0 timepoint.* A scatterplot will be produced to plot the GMFR in GMC of spike-protein antibodies against sample timepoints (D0, D28, D56, D84). For each patient, the first data point to be plotted will be at their D0 sample timepoint.

7.3 Exploratory endpoints

7.3.1 Vaccinated/Unvaccinated patients

The following endpoints will be reported separately for (i) vaccinated and (ii) unvaccinated patients, and (iii) across all patients:

- Sensitivity: the proportion of participants at each sample timepoint (D0, D28, D56, D84) with a positive detection of spike-protein antibodies out of those who had a positive neutralisation detection from the pseudovirus assay. Proportions will be reported alongside an exact two-sided 95% confidence interval.
- Specificity: the proportion of participants at each sample timepoint (D0, D28, D56, D84) with a negative detection of spike-protein antibodies out of those who had a negative neutralisation detection from the pseudovirus assay. Proportions will be reported alongside an exact two-sided 95% confidence interval.

7.3.2 Vaccinated patients with a second dose

- *Geometric fold rise (GMFR) in geometric concentration (GMC) of spike-protein antibodies from baseline (pre-second dose) to each timepoint (post-second dose).* A scatterplot will be produced to plot the GMFR in GMC of spike-protein antibodies against sample timepoints (D0, D28, D56, D84). For each patient, the first data point to be plotted will be at the last sample timepoint prior to their second dose.
- *GMFR of neutralising geometric mean titres (GMT) of spike-protein antibodies from baseline (pre-second dose) to each timepoint (post-second dose).* A scatterplot will be produced to plot the GMFR in GMT of spike-protein antibodies against sample timepoints (D0, D28, D56, D84). For each patient, the first data point to be plotted will be at the last sample timepoint prior to their second dose.

The number and proportion of patients with major and minor protocol deviations, alongside deviation details will be reported.

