4.1 Confidence Intervals and P values

No formal statistical hypothesis testing will be undertaken. All confidence intervals presented will be 95% and two-sided.

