4.3 Analysis populations

The analysis of the endpoints will involve the following populations:

- ***Patients with a completed blood test (Arm B)***

This population includes all patients who completed at least one blood test during the study.

- ***Unvaccinated patients (Arm B)***

This population includes all patients who did not receive a vaccine dose prior or during their last completed blood test in the study.

- ***Vaccinated patients (Arm B)***

This population includes all patients who received at least one vaccine dose prior to their D0 blood test.

- ***Vaccinated patients with a second dose (Arm B)***

This population includes all patients who received their second vaccine dose after their D0 blood test and prior to their last blood test in the study.

5. Study Population

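### SAP 7.3.2 shows fold rise after dose 2 by study visit only, not by time since the dose, and none of the four GMFR analyses states an estimator or a confidence interval

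*SAP*

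**What the plan says.** The second-dose population in SAP 4.3 is the set of Arm B patients who "received their second vaccine dose after their D0 blood test and prior to their last blood test in the study". SAP 6.3.2 and 7.3.2 define two exploratory fold rises for this group, one in spike-antibody concentration and one in neutralising titre. Each starts from a pre-dose-2 baseline chosen patient by patient: "For each patient, the first data point to be plotted will be at the last sample timepoint prior to their second dose". The only display is a scatterplot against D0, D28, D56 and D84.

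Two further GMFR endpoints are secondary. In SAP 7.2.1 (unvaccinated patients) the plotting rule is: "For each patient, the first data point to be plotted will be at the first sample timepoint at which they showed a positive antibody detection". In SAP 7.2.2 (vaccinated patients) it is: "For each patient, the first data point to be plotted will be at their D0 sample timepoint". Both are also scatterplots by visit.

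For the vaccinated proportions, but for no GMFR, the SAP adds a vaccine-based time scale. SAP 6.2.2 reports them "at time periods adjusted to the no. of days from 1st vaccine date".

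On precision, SAP 7.1, 7.2.1, 7.2.2 and 7.3.1 give each endpoint proportion an exact interval. For example, 7.3.1 says: "Proportions will be reported alongside an exact two-sided 95% confidence interval". The general rule in SAP 4.1 is: "All confidence intervals presented will be 95% and two-sided".

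**The concern.** There are two linked gaps.

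The first is the time axis in 7.3.2. The quantity is a response to dose 2, but it is shown by study day, and study day is not tied to dose 2. At a given visit, one patient may have been dosed a day earlier and another many weeks earlier. D28 or D56 may also be the baseline for one patient and a post-dose sample for another. What is read off the plot at a visit then depends on when patients were dosed as well as on how they responded. The SAP recognises this for the vaccinated proportions, which it re-times from the first vaccine date.

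The second is the summary itself. A geometric mean fold rise is a group quantity, but the plots are described point by point for each patient. The SAP does not say whether a mean is calculated, how it is calculated, or with what interval. Two statisticians following the text could produce different outputs, and neither need report a precision. SAP section 11 says that the study's goal has moved to serological response to infection and vaccination, so these are the analyses that quantify the size of that response.

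**Working it through.** The documents give no sample size or precision for any GMFR, so there is no planned figure to reproduce. The ±4.8% for Arm B in protocol 14.1 concerns a proportion.

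**Step 1. Days since dose 2 at each visit.**

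Inputs:
- dose 2 falls after the D0 sample and before the last sample (SAP 4.3);
- baseline is the last sample before dose 2 (SAP 7.3.2);
- Arm B visits are at D0, D28, D56 and D84, with ±10 days on the last three (protocol Table 3);
- assumption: no missed visit.

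With dose 2 between consecutive visits k and k+1, and a sample at visit j:
- maximum = latest day of visit j − earliest day of visit k;
- minimum = earliest day of visit j − latest day of visit k+1, or 0 when j is visit k+1.

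| Sample | Order after dose 2 | Dose 2 between | Nominal days | Days with windows |
|---|---|---|---|---|
| D28 | first | D0 and D28 | 0-28 | 0 to 38−0 = 38 |
| D56 | first | D28 and D56 | 0-28 | 0 to 66−18 = 48 |
| D56 | second | D0 and D28 | 28-56 | 46−38 = 8 to 66−0 = 66 |
| D84 | first | D56 and D84 | 0-28 | 0 to 94−46 = 48 |
| D84 | second | D28 and D56 | 28-56 | 74−66 = 8 to 94−18 = 76 |
| D84 | third | D0 and D28 | 56-84 | 74−38 = 36 to 94−0 = 94 |

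The D84 position can therefore hold points from 0 to 84 days after dose 2 nominally, or 0 to 94 days with the windows. These are limits that the definitions allow, not observed values. Missed visits would loosen the link between sample order and time: a first post-dose sample could then fall later than the table shows.

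**Step 2. What is specified for each type of endpoint.**

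| Analysis | Time scale | Estimator | Interval |
|---|---|---|---|
| Proportions, 7.1, 7.2.1, 7.3.1 | visit | proportion | exact 95% |
| Proportions, 7.2.2 | visit, and days from first vaccine | proportion | exact 95% |
| GMFR, 7.2.1 | visit, from first positive sample | not explicit | none stated |
| GMFR, 7.2.2 | visit, from D0 | not explicit | none stated |
| Two GMFRs, 7.3.2 | visit, from last sample before dose 2 | not explicit | none stated |

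The rule in SAP 4.1 fixes the level and sidedness of any interval that is presented. It does not say that a GMFR will have one.

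**Step 3. What an interval would look like.**

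For the antilog of the mean log10 ratio, the 95% CI is the GMFR multiplied and divided by 10^(t(0.975, n−1) × SD/√n). The SD of the log10 fold change and n are not in the documents, so the values below are assumptions shown over a range.

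| n | SD 0.3 | SD 0.5 | SD 0.7 |
|---|---|---|---|
| 10 | 1.64 | 2.28 | 3.17 |
| 20 | 1.38 | 1.71 | 2.13 |
| 40 | 1.25 | 1.45 | 1.67 |

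Example: n = 10 and SD = 0.5 gives 10^(2.262 × 0.5/√10) = 10^0.358 = 2.28. In a group that small, an observed doubling would have an interval from 2/2.28 = 0.88 to 2 × 2.28 = 4.56, which includes no rise. A bare point estimate would not show this.

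**The case against.** The best defence is that 7.3.2 is exploratory, that SAP 4.1 rules out formal hypothesis testing, and that a scatterplot of individual ratios averages nothing across times since dose. On that reading no interval is needed for a point, and each patient's baseline can be seen. Part of this stands: no error rate is at risk, and if only individual points are shown, no pooled number is distorted. But the endpoint is named as a geometric mean, and the text does not choose between the two readings. Nor does it say that points are joined or labelled. Even joined points would show sample order, not days since the dose.

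It could also be said that section 11 withdrew the exploratory endpoints. SAP 6.3.3 applies that to its own list (antigen dynamics, HLA-KIR, immune phenotype, transcriptome). Section 7.3.2 keeps a full method and remains in the plan.

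SAP 6.2.1, 6.2.2 and 6.3.2 allow each GMFR analysis to be postponed until its data arrive. That bears on urgency but supplies no estimator.

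A reader might infer that the SAP gives no calculation at all. That goes too far: population, reference point, comparison timepoints and the geometric scale are stated. What is missing is an explicit estimator, an interval and a rule for values below the assay limit.

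**Conclusion.** Both gaps are present in the text. The visit axis in 7.3.2 can mix samples taken up to 84 days after dose 2 nominally (94 with windows) with samples taken just after it, and a clearer display is available at little cost. The missing estimator and interval affect all four GMFR analyses, including the secondary ones in 7.2.1 and 7.2.2, and do not depend on when doses were given.

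A reader might go further and infer that the post-dose-2 results are shown to be distorted. The documents do not support that. They give neither the dose-2 dates nor the size of the second-dose group. If second doses cluster at a similar point in follow-up, the timing effect may be nil; if they are widely spread, it may be substantial. Nor does the point reach the primary endpoint, which is a set of proportions by visit with exact intervals. It should be treated as an inexpensive improvement to how descriptive results are defined and read. The day limits assume no missed visit, and the interval factors rest on assumed SDs and group sizes.

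**What to change.** 1. **SAP 7.3.2.** Keep the visit plots. Add, for each of the two fold rises, the individual values by actual days since dose 2 (sample date minus dose-2 date). Where the exact dose date is missing, label the point as first, second or third post-dose sample. This needs only the order of dose and samples, which the baseline rule already requires. It is coarser, because with the windows the three ranges overlap.

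2. **SAP 7.2.1, 7.2.2 and 7.3.2.** For each GMFR, state that it is the geometric mean of within-patient fold changes (antilog of the mean log ratio). Report it with a two-sided 95% CI and n. Leave reference points, where the fold is 1 by definition, out of the average. Apply one stated rule to values below the assay limit and report how many are affected. This matters most in 7.2.2 and 7.3.2, which are not restricted to antibody-positive patients.

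Cost: SAP wording, the added display in 7.3.2 and one summary line per analysis. Dose-2 dates may have to be retrieved: protocol Table 3 has no vaccination item for Arm B and records concomitant medications only at D0, although protocol section 10 allows data to be supplemented from the electronic records. Intervals will be wide in small groups. If any GMFR analysis has already been run, the addition should be dated and labelled as such.

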7.4 Timing of analyses

Analyses for all endpoints will be performed and reported once the study has closed, final set of lab data have been received, and a database lock has been applied.

8. References

- 1) Walsh, Edward E et al. "Safety and Immunogenicity of Two RNA-Based Covid-19 Vaccine Candidates." *The New England journal of medicine* vol. 383,25 (2020): 2439-2450. doi:10.1056/NEJMoa2027906

9. Statistical Packages

All analyses will be performed using STATA 17.0 or subsequent versions.

10. Data Management & Central Statistical Monitoring Plan

All data prior to analysis should have been cleaned and checked as per SOP ST08 (Procedures for Statistical Analyses and Reporting of Clinical Trials, Final and Interim in RM/ICR Sponsored Trials) and SOP ST09 (Procedures for Central Statistical Monitoring in RM/ICR Sponsored Trials).

11. Changes to the protocol

As the COVID-19 pandemic evolved, several factors had an impact on the study, and consequently on some of the endpoints. These had to be taken into account when drafting the SAP, which led to the following changes:

1. Arm A: this arm will be excluded from any analysis since recruitment was halted, with only one Arm A patient registered to the study at the time of study closure.
2. Changes in technology\assay: the statistical report will only look at positive detection of IgG specific antibodies and not IgM antibodies as stated in the protocol.
3. PV neutralisation results will be used in both the sensitivity and specificity analyses, instead of lateral flow test results.
4. Some of the analyses will now take patients' vaccination status into account.
5. As the goal of the study has shifted towards analysing serological responses to previous SARS-CoV-2 infection and vaccination, the exploratory endpoints will no longer be performed.

CARDS

Cancer: Rapid Diagnostics and Immune assessment for SARS-CoV-2 (COVID-19)

Study Statistician

[name]

Digitally signed by
[name]
Date: 2021.12.09
14:37:33 Z

[name]

Date

Reviewer Statistician

[name]

Digitally signed by
[name]
Date: 2021.12.09
09:52:48 Z

[name]

Date

